***fMRI data:***

SPM5 (Wellcome Department of Cognitive Neurology, London, UK) will be employed for motion correction and used to normalize the EPI BOLD images to a standard space using a 12 parameter linear transformation. The images will be then spatially smoothed using an 8.0 mm Gaussian kernel. Finally, the statistical package contained within SPM5 will be used to estimate the effects of condition at each voxel according to the general linear model. The analysis will be entered into SPM5 as an epoch design of the fixed response/box car form convolved with canonical HRF, reflecting the appropriate activation and rest periods within the total scanning period. Images will be high-pass filtered at 128 s to remove low- frequency drifts in blood oxygen level-dependent signal.

Percent signal change (after vs. before) will be compared statistically between the two groups using unpaired two-sample t-tests between the robotic and aerobic groups. A repeated measures ANOVA will be performed with the dependent variable being the percent signal change and between subjects factor Group (robotic therapy, aerobic therapy), and within subject factor Time (before and after training).

Along with percent signal change over time, we will also compute region-wise laterality index. ROIs will be predefined in each hemisphere. For each ROI, laterality index (LI) will be defined as: Number of activated voxels in the affected hemisphere / [voxels in the left hemisphere + voxels in the right], thus giving LI for each ROI. LI = 0.5 indicates symmetrical activation; LI < 0.5 indicates an activation deficit on the affected side, and LI > 0.5 indicates increased activation of the affected side. This index will provide a way of

understanding the contribution of each brain area (ROI) to the overall task-related activation in one session and changes in laterality over time. The percent signal change and LI are purely quantitative measures, in order to ensure that change in plasticity over time is captured adequately and does not rely on individual fMRI reader's abilities to gauge these changes simply on the basis of a "visual read" of the fMRI scans.

fMRI data is in the form of many voxels that are traditionally analyzed separately. This analysis needs to be corrected for the thousands of statistical tests performed. Corrections need to consider the spatial nature of fMRI data so simple schemes, such as the Bonferroni correction, are not appropriate. A method that controls the family-wise error (FWE) balances the statistical threshold with a minimum cluster size to produce an overall p-value for an activation cluster (Forman et al. 1995). We will use this FWE technique to correct our functional data for multiple comparisons.

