### ***Secondary outcomes***

The change in strength of brain activity in affected regions of interest (ROI) within the brain, and the change in laterality index (LI) comparing the same ROI in affected and unaffected hemispheres. Regions of interest include the primary sensorimotor cortex, the supplementary motor area, and the cerebellum.

Normative data on the progression of motor learning (behavioral measures) and brain activity (fMRI) in control subjects of similar age to the stroke-prone population (50-85 years).

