### ***Functional MRI scans:***

- Participants who will undergo an MRI scan will be screened for MRI eligibility using the UW Department of Radiology's standard clinical MRI screening form.
- All patients in the study will be scanned at two time points (before and after intervention).
- Healthy Normals in the Typical Comparison group will be scanned once.
- Healthy Normals in the Pilot group will not be scanned.

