### **Data Processing/Data Analysis**

#### ***Behavioral Data:***

For the analysis of pre- and post- measures on the behavioral data, we will perform repeated measures ANOVA tests with time as the independent variable and score on

each behavioral test as the dependent variable.

In order to assess the overall effect of the rehabilitation protocol, we will perform multiple regression analyses to determine the extent to which data from each modality explains the proportion of the variance in the behavioral outcomes. The dependent variable is the score on the behavioral test and the predictors are the task tracking performance (error) in EMG and foot force during the last training session, and the percent signal change in targeted brain areas from the fMRI data.

In addition, we will also perform a multivariate ANOVA to examine the mixed model with Time of testing (pre, post) as a within subject factor, Group (robotic therapy, aerobic therapy) as the between-subject factor, and dependent variables of percent signal change from the fMRI data and each of the behavioral scores. This will help us to determine if there is a significant difference between the groups in terms of behavioral performance and functional activations and also to determine whether these dependent measures change over time.

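### No between-arm analysis of fMRI percent signal change adjusts for the pre-training scan, which usually costs precision that ANCOVA would recover from data already planned

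*Combined protocol and SAP*

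**What the plan says.** The Secondary outcomes section names two imaging outcomes for patients: "The change in strength of brain activity in affected regions of interest (ROI) within the brain", and the change in laterality index for the same regions. The Functional MRI scans section plans one scan before and one after training for every patient.

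Three analyses in Data Processing/Data Analysis compare percent signal change between the arms:

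- fMRI data, t-test: "Percent signal change (after vs. before) will be compared statistically between the two groups using unpaired two-sample t-tests between the robotic and aerobic groups".
- fMRI data, ANOVA: "A repeated measures ANOVA will be performed with the dependent variable being the percent signal change and between subjects factor Group", with Time (two levels) as the within-subject factor.
- Behavioral Data, multivariate ANOVA: "Time of testing (pre, post) as a within subject factor, Group (robotic therapy, aerobic therapy) as the between-subject factor", with percent signal change among the dependent variables.

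In the two ANOVAs the pre-training scan is one of the two responses. It is a covariate in none of the three, and no baseline-adjusted between-arm model appears elsewhere in the documents.

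For the other imaging outcome, the fMRI data section says "Along with percent signal change over time, we will also compute region-wise laterality index" and defines the index, but states no between-arm test. Subject randomization balances on sex and Fugl Meyer severity, not on baseline activation.

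**The concern.** The secondary objective is a comparison of plasticity between robotic and aerobic pedaling, and the plan expects about 16 completers per arm. In arms that small, baseline activation can differ by chance. A change score subtracts the whole baseline value, and so carries the full scan-to-scan noise of both scans into the comparison. ANCOVA subtracts only the part of the baseline that predicts the follow-up scan.

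The list of analyses also looks richer than it is. For the between-arm question, the t-test and the Group by Time term give one answer twice. The plan does not say which ANOVA term answers the secondary objective. A reader who took the Group main effect would be looking at a diluted quantity. At stake are the precision of the imaging comparison and the clarity of which result counts.

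**Working it through.** **The plan's own figures.** Sample Size uses n per group = 2 × ((z(1−α/2) + z(β)) × σ / d)². For the 6MWT (154.3, SD 171.1 m), two-sided: 2 × (2.80 × 171.1 / 154.3)² = 19.3, so 20. One-sided: 2 × (2.49 × 171.1 / 154.3)² = 15.2, so 16. Allowing for dropout, 16 / 0.80 = 20 enrolled per arm. These agree with the plan. The stated fMRI figure of 12 subjects cannot be reproduced, because no effect size or SD is given for it.

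**Inputs.** From the documents: 16 evaluable per arm (N = 32), two scans per patient, 1:1 randomisation. Assumed, because the documents do not give them: the pre-post correlation ρ of a region's percent signal change (0.2, 0.5, 0.8); equal SD at both scans; a common slope in both arms; a true arm difference δ of 1 SD or 0.5 SD of the per-scan value.

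**Step 1: the two tests coincide.** With two time points, the Group by Time interaction contrasts the arms' mean changes using the variance of the changes, so F = t². On one simulated data set with 16 per arm, both came to 0.006768.

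**Step 2: the Group main effect.** It compares the arms on the average of the two scans. The treatment difference is 0 before training and δ after, so the expected contrast is (0 + δ)/2 = δ/2, with per-patient variance (1 + ρ)/2 in units of SD². At δ = 1 SD and ρ = 0.5, power is 35%, against 78% for the interaction.

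**Step 3: precision.** In units of SD²:

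- change score: 2(1 − ρ)
- ANCOVA: (1 − ρ²) × (N − 3)/(N − 4) = (1 − ρ²) × 29/28, where the last factor is the cost of estimating the slope
- ratio: (1 + ρ)/2 × 29/28

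The worth of 16 per arm is 16 divided by the ratio. Power comes from the noncentral t, two-sided 0.05, with noncentrality δ / √(variance × 2/16), on 30 degrees of freedom for change and 29 for ANCOVA.

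| Assumed ρ | Variance, change | Variance, ANCOVA | Ratio | 16 per arm with ANCOVA is worth, under the planned test | Power at 1 SD, change → ANCOVA |
|---|---|---|---|---|---|
| 0.2 | 1.60 | 0.994 | 0.62 | 25.7 per arm | 58% → 78% |
| 0.5 | 1.00 | 0.777 | 0.78 | 20.6 per arm | 78% → 87% |
| 0.8 | 0.40 | 0.373 | 0.93 | 17.2 per arm | 99.1% → 99.4% |

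At δ = 0.5 SD and ρ = 0.5, power moves from 28% to 34%.

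**Step 4: break-even.** The ratio equals 1 when ρ = 2 × 28/29 − 1 = 0.93. Above that, ANCOVA is slightly the noisier method at this size.

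**Step 5: simulation check.** With 10,000 trials at each ρ, the simulated variance ratios were 0.67, 0.77, 0.89 and 0.99 at ρ = 0.3, 0.5, 0.7 and 0.9. The formula gives 0.67, 0.78, 0.88 and 0.98.

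**The case against.** The strongest reply is that nothing here is invalid. A change-score comparison is unbiased under randomisation, it matches an outcome worded as a change, and it concerns a secondary outcome in a self-described pilot whose size was set by gait measures. All of that stands. So does the point that the gain depends on a correlation and an effect size absent from the documents, and runs from material to negligible.

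Some stronger readings are tempting but are not supported:

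- *A reader might infer that the ANOVA is wholly redundant.* Only its Group by Time term duplicates the t-test. It also gives a Time effect, which an unpaired t-test on change cannot, and the Behavioral Data section names change over time as one aim of its parallel model.
- *A reader might infer that a change score is never more precise than ANCOVA.* That is a large-sample result. At 16 per arm it fails above a correlation of about 0.93.
- *A reader might infer that the t-test also covers the laterality index.* The stated tests name percent signal change only. The index has no between-arm test, which is a separate gap.
- *A reader might take the after-versus-before wording as a ratio to baseline activation, which would be unstable where baseline is near zero.* The very next sentence treats percent signal change as a value measured at each time point, and so does the Behavioral Data section. The wording could be tighter, but the text does not favour the ratio.

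**Conclusion.** The point holds as one of precision and clarity, not of bias. Percent signal change is compared between arms without adjustment for a baseline scan planned for every patient, and two of the listed results are the same test. At 16 per arm, ANCOVA would cut the variance of the arm difference by about 38%, 22% and 7% at assumed correlations of 0.2, 0.5 and 0.8, with no gain near 0.93. These figures rest on equal SDs at the two scans, a common slope and an assumed correlation. The power figures also rest on an assumed effect of 1 SD or 0.5 SD. The gait-based sample size is unaffected.

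**What to change.** In the fMRI data section, define percent signal change as the task-versus-rest value at each scan. For each region of interest, make the between-arm analysis a regression of the post-training value on Group, with the same region's pre-training value as covariate. Report the adjusted robotic-minus-aerobic difference with its 95% confidence interval. State that the same model applies to the laterality index.

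Drop the unpaired t-test. Keep the repeated-measures ANOVA only for the Time question (change within groups), and say so. In the Behavioral Data section, state that the between-arm conclusion for percent signal change comes from the baseline-adjusted model, not from the multivariate Time by Group ANOVA.

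The cost is a change of wording and one degree of freedom per model. No new data are needed.

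### The laterality index formula leaves the word activated out of its denominator, and in its evidently intended form it moves with signal-to-noise and threshold whenever activation is asymmetric

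*Combined protocol and SAP*

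**What the plan says.** Under Secondary outcomes, the plan lists "the change in laterality index (LI) comparing the same ROI in affected and unaffected hemispheres" beside the change in strength of activity in affected regions. The regions named are primary sensorimotor cortex, supplementary motor area and cerebellum.

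Under Data Processing/Data Analysis, fMRI data, it says "ROIs will be predefined in each hemisphere" and gives LI for each as "Number of activated voxels in the affected hemisphere / [voxels in the left hemisphere + voxels in the right", where the bracket closes. It then interprets the result: "LI = 0.5 indicates symmetrical activation; LI < 0.5 indicates an activation deficit on the affected side". Values in the upper half of the scale are given a meaning as well: "LI > 0.5 indicates increased activation of the affected side". It supports the choice by saying that "The percent signal change and LI are purely quantitative measures", so that no reader's visual judgement is involved.

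The same section later describes a family-wise error method that "balances the statistical threshold with a minimum cluster size to produce an overall p-value for an activation cluster". It gives no voxel threshold and no cluster size, and it does not say whether this method decides which voxels count as activated for LI. ROI sizes are not given, and there is no rule for an ROI with no activated voxels.

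**The concern.** The formula and its interpretation do not agree. An analyst who follows the printed text would report symmetrical patients as having an affected-side deficit. An analyst who follows the interpretation has to supply a missing word and choose a threshold.

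The corrected formula still has a weakness. A count of voxels above a cut-off reflects how far each side's statistics lie from that cut-off as well as the relative strength of the two sides. If overall signal-to-noise changes between the two scans, the weaker and stronger sides gain or lose voxels at different rates, and LI moves although the true ratio has not. Overall signal could plausibly change here: patients step or imagine a task in the scanner, and the scanning protocol straps the torso because motion degrades the images. A change in LI is meant to show plasticity, so a change that comes only from signal quality could be misread as reorganisation.

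**Working it through.** **1. Does the stated symmetry value of 0.5 reproduce?** Let *a* voxels be active on each side, in ROIs of 500 voxels per side (an assumed size).

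- Activated voxels in the denominator: LI = a/(a + a) = 0.5 for any a > 0. The plan's figure reproduces.
- All voxels in the denominator, as printed: LI = a/(500 + 500). For a = 20, 100, 300 and 500 this gives 0.02, 0.10, 0.30 and 0.50. The plan's figure reproduces only when every voxel is active.

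**2. Upper limit.** As printed, the maximum is the affected ROI's share of all voxels in the pair: 500/1000 = 0.50 for equal ROIs, 550/1000 = 0.55 for 550 against 450, and 450/1000 = 0.45 for the reverse. With activated voxels in the denominator, the maximum is 1.

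**3. No voxel passes.** As printed, LI = 0/1000 = 0, which would be read as a complete deficit. With activated voxels in the denominator, LI = 0/0 and is undefined.

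**4. Dependence on signal, activated-voxel denominator.** The documents give no voxel means, SD or threshold, so all of these are assumptions. Take voxel t-values as normal with SD 1, mean 4 on the unaffected side and 3 on the affected side (true ratio 3:4, amplitude LI = 3/7 = 0.43). The share passing threshold *c* is 1 − Φ(c − mean), and LI = affected share/(affected share + unaffected share). At the second scan both means rise by 25%, to 5 and 3.75, so the ratio is unchanged.

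| Threshold | Scan 1 shares (affected, unaffected) | LI | Scan 2 shares | LI | Shift |
|---|---|---|---|---|---|
| 4.5 | 0.067, 0.309 | 0.178 | 0.227, 0.691 | 0.247 | 0.07 |
| 4.0 | 0.159, 0.500 | 0.241 | 0.401, 0.841 | 0.323 | 0.08 |
| 3.1 | 0.460, 0.816 | 0.361 | 0.742, 0.971 | 0.433 | 0.07 |

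The choice of threshold alone moves the scan 1 value from 0.18 to 0.36.

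**5. How far does this depend on the assumptions?**

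- If every t-value is scaled by 1.25, so that the SD also becomes 1.25, the shifts are 0.117, 0.107 and 0.067.
- With an affected-to-unaffected ratio of 0.8 and threshold 3.09, LI is 0.331, 0.346, 0.399 and 0.489 at unaffected means of 2, 3, 4 and 6.
- With the same ratio and threshold 4.5, LI falls from 0.231 to 0.211 as the mean rises from 2 to 3.
- At 3:4, threshold 3.1 and unaffected mean 1, a 25% rise takes LI from 0.344 down to 0.322.
- With a ratio of 1.0, LI is 0.500 at every signal level and threshold tried.
- Under the printed denominator, LI drifts even at perfect symmetry: 0.069, 0.232, 0.409 and 0.499 at means of 2, 3, 4 and 6 (threshold 3.09, equal ROIs).

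**6. The alternative.** For a normal voxel with mean *m* and SD 1, the expected positive part is mΦ(m) + φ(m). Base LI on the sum of positive values at 3:4, with equal ROIs. At unaffected means of 4 and 5 it is 0.429 both times. At means of 1 and 1.25 it is 0.4485 and 0.4422, a change of 0.006. Averaging only the positive voxels behaves less well: 0.43, 0.44, 0.47 and 0.49 at means of 4, 2, 1 and 0.5.

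**The case against.** The strongest reply is that the denominator is a slip of one word. The interpretation that follows it makes the intention plain, percent signal change is analysed separately with its own between-group tests, and this is one secondary outcome in a pilot. That stands as a limit on severity. It does not remove the signal dependence, which remains after the word is inserted. Nor does the absence of a shift at symmetry settle the matter: the trial enrols patients with unilateral deficits, and the plan uses LI to detect asymmetry.

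Several stronger readings are tempting, and the documents do not support them.

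- A reader might infer that LI is both undefined when nothing passes and capped at 0.5. These belong to different denominators and cannot hold together. The cap also needs an affected ROI no larger than its counterpart.
- A reader might infer that better signal always looks like recovery. Step 5 shows reversals at weak signal.
- A reader might infer that many patients will lose their LI, and not at random. That needs both sides to be empty. With independent voxels of mean 1 on both sides and threshold 3.09, the probability is 0.69 for 10 voxels per side and 0.16 for 50. At mean 2 it is 0.05 and about 0. The documents fix none of these inputs, so the frequency is unknown.
- A reader might infer bias between the arms. Patients are randomised, and a change in scan quality common to both arms favours neither. A differential change would be needed, and nothing in the documents shows one.
- A reader might take the family-wise error method as the rule that defines activated voxels for LI. The text does not make that link.

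**Conclusion.** The printed formula contradicts its own interpretation and should be corrected. With equal ROIs, it puts symmetrical activation below 0.5 unless every voxel is active, and its upper category cannot be reached. This follows from the text and simple arithmetic; the only assumption is ROI size.

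Under the evidently intended denominator, LI depends on overall signal and on an unstated threshold whenever activation is asymmetric. That dependence follows from counting above a cut-off. The illustrated shifts of about 0.07 to 0.08 rest on an assumed normal voxel model with the SD held at 1. They show that the effect can be appreciable but do not estimate its size in this trial. The case of no active voxel on either side needs a rule, although how often it would occur cannot be derived.

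The correction is worth making before analysis. It does not touch the primary gait outcomes or the percent-signal-change analysis.

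**What to change.** In the fMRI data section:

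1. Insert the word activated in both denominator terms of the voxel-count LI.
2. Make the main LI the sum of positive t-values (or of positive signal change) over the affected ROI, divided by the same sum over both sides. Use the same size-matched ROI masks at both scans, because a sum grows with the number of voxels. A value of 0.5 then means symmetry. Use the sum rather than the mean of positive values, for the reason shown in step 6.
3. Keep the voxel-count LI as a sensitivity analysis, with one threshold (and cluster size, if used) stated in advance and applied at both scans, and a written rule for zero counts on one or both sides.

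The cost is a short rewrite of one definition and some extra extraction from scans already planned. The main LI will be less directly comparable with published voxel-count indices, which the sensitivity version partly covers. It should be described as less dependent on threshold rather than immune to signal level, because some drift towards 0.5 remains at very low signal.

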### ***Data from Healthy Normals:***

The EMG data from healthy normals will help us to determine if the subjects are able to learn novel motor tasks that decompose traditionally synergistic muscle groups during cycling, and whether they show any handedness bias. The fMRI data from normals will show traditional areas of activation while performing or imagining a motor task; the average map derived from these subjects will serve as a control for the patients.

### **Sample Size**

Below we give sample size calculations based on the gait outcome measures (six-minute walk test (6MWT), self-selected walking speed (SSWS) and fastest comfortable walking speed (FCWS)), as well as the expected changes in brain activations:

The sample size required per group is computed using the following formula:  $N$  (per group) =  $2 * ( (z(1-\alpha/2) + z(\beta)) * \sigma / d )^2$ , where  $d$  is the expected difference in outcome value, post- vs. pre-training;  $\sigma$  is the estimated standard deviation;  $\alpha$  is the alpha error we would like to control; and  $\beta$  is the statistical power. Here we set a statistical goal of 80% power ( $\beta = 0.80$ ,  $z(\beta) = 0.84$ ) and  $\alpha$  level 0.05 ( $z(1 - \alpha/2) = 1.96$ ).

Based on a recent study of locomotor rehabilitation in chronic stroke (Bowden et al., 2013), we expect: a difference in 6MWT of 154.3 +/- 171.1 meters; a difference in SSWS of 0.21 +/- 0.13 m/s; and a difference in FCWS of 0.18 +/- 0.15 m/s. These give sample size estimates of 20, 6 and 11 subjects, respectively. This sample-size estimate is conservative, using a two-tailed test when in fact we expect to test explicitly for an

increase (one-tailed test). For a one-tailed distribution (using  $z(1 - \alpha) = 1.65$ ), sample size estimates are 16, 5 and 9 subjects.

For fMRI signal changes at the single voxel level, we expect to achieve statistical power of 80% with a significance cutoff of alpha = 0.05 using a sample size of 12 subjects, as reported in literature (Desmond and Glover, 2002).

The maximum of all sample size estimates for two-tailed tests is 20 subjects. However, the outlier is the 6MWT; without this, the maximum would be 12 subjects. Balancing the practical (budgetary, time) need for a small sample with the need to capture as many metrics as possible, **we choose a sample size of 16**. This sample size just captures the expected change in 6MWT (in a one-tailed test) and is well above the necessary sample size for other outcomes. Based on previous experience, we estimate a 20% dropout rate (due to patients not being able to complete all sessions, or not coming back for post training evaluation). We therefore propose to enroll 20 patients per group (robotic, aerobic), for a total of 40 patients.

Up to 20 healthy controls will be enrolled to form a normal data set of similar size to each patient group.

Up to 60 additional healthy subjects will be enrolled for pilot testing. Pilot subjects are not a statistical group, so no specific sample size is required.

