## **Study Objectives**

### ***Primary objective***

To examine the effect of a robotic pedaling therapy program that rewards coordinated foot pedal forces and EMG patterns on lower-limb function during pedaling and walking, in comparison to an aerobic pedaling task.

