### **Aerobic Training Group (Control Group): Procedure**

Patients in the Control group will perform an identical protocol to that used by the Robotic group, except that the robotically-incentivized pedaling exercise will be replaced with an aerobic therapy program. This intervention will emulate an established form of motorized pedaling therapy similar to that used in commercial motorized exercise bikes to improve underlying cardiovascular unfitness contributions to gait impairment. This therapy implements a simple version of assist-as-needed and constant-velocity control. The patient's target pedaling speed (e.g. 20 rev/min (to be finalized through pilot tests: range 15-50 rev/min) and power level (set by heart rate to require approximately 50-70% of maximal oxygen uptake, estimated individually for each patient) are set at the beginning of each session and a motor provides assistance or resistance to compensate for the performance of the patient. The exercise will be performed in this mode for 30 minutes per training session.

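### The sample size puts a pre-to-post gain into a two-group formula, so no power is shown for robotic versus aerobic, and 16 per arm reaches 80% for 6MWT only one-tailed

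*Combined protocol and SAP*

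**What the plan says.** All references are to the combined protocol and SAP.

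- **Formula and d.** Sample Size gives a per-group N with a leading factor of 2, the form for two independent groups. It says that d "is the expected difference in outcome value, post- vs. pre-training".
- **Inputs.** These come from a cited study of locomotor rehabilitation in chronic stroke: "a difference in 6MWT of 154.3 +/- 171.1 meters", with 0.21 ± 0.13 m/s for SSWS and 0.18 ± 0.15 m/s for FCWS.
- **Results.** The estimates are 20, 6 and 11 two-tailed, and 16, 5 and 9 one-tailed. "The maximum of all sample size estimates for two-tailed tests is 20 subjects". The plan treats the 6MWT as the outlier and chooses 16: "This sample size just captures the expected change in 6MWT (in a one-tailed test"). It then enrols 20 per group to allow for 20% dropout.
- **Sidedness.** Of the two-tailed figures it says: "This sample-size estimate is conservative, using a two-tailed test when in fact we expect to test explicitly for an" increase.
- **Question asked.** The primary objective concerns the effect of robotic therapy "on lower-limb function during pedaling and walking, in comparison to an aerobic pedaling task". The Behavioral Data analysis plan has "Group (robotic therapy, aerobic therapy) as the between-subject factor" and time of testing as the within-subject factor.
- **Comparator.** Of the aerobic arm, the control-group procedure says: "This intervention will emulate an established form of motorized pedaling therapy". It adds that such therapy is meant to act on the part of gait impairment that comes from poor cardiovascular fitness.

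**The concern.** A pre-to-post gain in one arm is not the difference in gain between two arms. Used as d in a two-group formula, it gives the power for robotic versus aerobic only if the aerobic arm's mean change is zero. The plan does not assume this, and its own account of the control as an active pedaling therapy points the other way. The documents give neither an expected aerobic gain nor an expected robotic-minus-aerobic difference.

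The other reading is that d was meant for a pre-post test within an arm. Research Design and Methods does describe each patient as their own control, and a time-only ANOVA is listed. On that reading the factor of 2 does not belong, and the between-arm primary objective has no power statement at all.

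The second issue is sidedness. The 6MWT is the measure that sets n = 16, and the plan's own two-tailed requirement for it is 20 completers per arm. The one-tailed basis for 16 is disclosed but does not reach the analysis section. That section lists repeated-measures ANOVA and MANOVA for the gait measures, whose F tests are non-directional. The unpaired t-tests it lists are for fMRI signal change, with no one-tailed level stated.

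The stated 80% goal is easily read as applying to the main comparison. If the group difference in 6MWT is then non-significant, nothing in the plan tells the reader what difference the trial could have detected.

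**Working it through.** **Inputs (Sample Size section).** d/σ: 6MWT 154.3/171.1 = 0.902; SSWS 0.21/0.13 = 1.615; FCWS 0.18/0.15 = 1.200. Two-tailed z 1.96, one-tailed z 1.65, power z 0.84. Evaluable n = 16 per arm; enrolled n = 20.

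**1. The plan's own figures.** N = 2 × ((z + 0.84) × σ/d)².

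| | Two-tailed | Stated | One-tailed | Stated |
|---|---|---|---|---|
| 6MWT | 19.28 | 20 | 15.25 | 16 |
| SSWS | 6.01 | 6 | 4.75 | 5 |
| FCWS | 10.89 | 11 | 8.61 | 9 |

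Dropout: 16/0.8 = 20. The arithmetic reproduces. (SSWS at 6.01 would strictly round up to 7; this has no consequence.) It reproduces only with the two-group factor of 2.

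**2. Power at 16 per arm, two-sided 0.05, if the aerobic arm gains nothing.** By the plan's normal approximation, power = Φ(d/σ × √(16/2) − 1.96):

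- 6MWT: Φ(2.551 − 1.96) = 72%
- SSWS: Φ(4.569 − 1.96) = 99.5%
- FCWS: Φ(3.394 − 1.96) = 92%

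With two time points, the Group-by-Time test is equivalent to a two-sample t-test on change scores. The noncentral t with 30 degrees of freedom gives 69%, 99% and 91%. If all 20 per arm complete, the 6MWT figure is 79% (81% by the plan's formula).

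**3. Power if the aerobic arm also improves.** With an aerobic gain equal to a share f of the stated gain, the between-arm difference is (1 − f) × d. The shares are assumptions, because the plan gives none.

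| Aerobic share f | 6MWT two-sided | SSWS two-sided | FCWS two-sided | 6MWT one-tailed |
|---|---|---|---|---|
| 0 | 69% | 99% | 91% | 80% |
| 1/4 | 46% | 91% | 69% | 59% |
| 1/2 | 23% | 60% | 38% | 35% |

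The last column shows that one-tailed testing does not repair d.

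**4. Difference detectable with 80% power, 16 per arm, two-sided t-test.** This is 1.024 × σ.

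- 6MWT: 175 m, or 114% of the stated gain. No aerobic gain can be tolerated.
- SSWS: 0.133 m/s, or 63% of the stated gain. An aerobic gain up to 37% (0.077 m/s) can be tolerated.
- FCWS: 0.154 m/s, or 85% of the stated gain. An aerobic gain up to 15% (0.026 m/s) can be tolerated.

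**5. Expected 95% CI half-width for the between-arm difference.** t(0.975, 30) × σ × √(2/16) = 2.042 × 0.3536 × σ, which is 124 m, 0.094 m/s and 0.108 m/s.

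**6. The within-arm reading.** A paired test with n = 16, two-sided, has 92% power for 6MWT. The number is ample for that test, but it says nothing about robotic versus aerobic.

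**7. Sensitivity to the meaning of the ± values.** Steps 2 to 6 take them as SDs of change. If they are SDs of scores at a single visit, the SD of change is σ × √(2(1 − r)), where r is the pre-post correlation. The documents do not give r. For 6MWT with zero aerobic gain, two-sided power is 55% at r = 0.3, 69% at 0.5, 89% at 0.7 and 97% at 0.8. At r = 0.8 and an aerobic share of one quarter it is 83%.

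**The case against.** **Every power figure depends on what the ± values are.** This stands. If they are single-visit SDs and the pre-post correlation is high, 6MWT power is well above 69%; if the correlation is low, it is worse. The percentages are therefore conditional. The mismatch between d and the objective does not depend on them.

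**The one-tailed choice is disclosed.** It is: the plan prints both sets of numbers and presents 16 as a compromise with budget and time. The analysis section is silent on sidedness rather than contradictory, and specifying a directional test there would also reconcile the two. That would leave d unchanged, however, and the ANOVA and MANOVA F tests as listed are not directional. SSWS and FCWS do not need the one-tailed choice at the full stated d.

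**This is a pilot that looks ahead to a full-scale study.** A pilot need not be powered for its comparison. This one sets an 80% goal and derives its n from it, so the derivation should match the objective. Dropouts may also be replaced at the PI's discretion, so completers could exceed 16 per arm, but the 6MWT then reaches only about 79% even with no aerobic gain.

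**A confidence interval would reveal low precision whatever power was stated.** This is correct, and is why the fix asks for expected interval widths. The plan does not currently provide them.

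**Conclusion.** The point holds. The stated 80% is not shown for the primary robotic-versus-aerobic comparison: on one reading it needs an aerobic gain of zero, and on the other it concerns a different test. This conclusion needs no assumption beyond the plan's text.

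The size is conditional on the ± values being SDs of change. At 16 completers per arm, two-sided, the 6MWT falls short of 80% even in the most favourable case. FCWS keeps 80% only while the aerobic arm gains less than about 15% of the stated amount, and SSWS up to about 37%. The separate claim that the two-tailed calculation is conservative does not support 16, because for the 6MWT the plan then chooses a number below its own two-tailed requirement of 20.

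**What to change.** Keep 20 per arm and restate the Sample Size section.

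1. Define d as the between-arm difference in pre-to-post change and σ as the SD of change. Say whether the quoted ± values are SDs of change. If they are not, state the pre-post correlation used.
2. Remove the one-tailed justification of 16 and the remark that the two-tailed calculation is conservative, so that the calculation matches the group tests in the analysis section.
3. For all three gait measures, report the between-arm difference detectable with 80% power at 16 completers per arm, two-sided, with the expected 95% CI half-width. If the ± values are SDs of change, the detectable differences are about 175 m (6MWT), 0.13 m/s (SSWS) and 0.15 m/s (FCWS), and the half-widths about 124 m, 0.09 m/s and 0.11 m/s.
4. Note that the fMRI figure of 12 subjects is single-voxel power at alpha 0.05 with no multiplicity correction stated for that calculation, and is not shown to be power for the between-arm comparison.

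The cost is rewording, with no added patients or visits. The stated power becomes less favourable, and unless the SD of change proves smaller than 171.1 m, the 6MWT can no longer be described as having 80% power.
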